13.4.1. TUBE PATENCY

Tube Patency is the proportion of subjects in the pivotal cohort FAS, in which a Tusker Medical tube was successfully placed, with functional tube patency in all successfully treated ears at the 3-week post-procedure follow-up visit.

The statistical test for the pivotal cohort Tube Patency secondary endpoint is a hypothesis test for the proportion of subjects with functional tube patency in all successfully treated ears at the 3-week follow-up visit against a tube patency performance goal. The mid-P^{71,72,73} method for a single proportion will be used to test

$$H_0: p \leq 80\%$$

Vs.

$$H_a: p > 80\%.$$

This endpoint will be considered met if the p-value from the test is less than 0.025.

13.4.2. TUBE RETENTION

Tube Retention is the proportion of subjects in the pivotal cohort FAS, in which a Tusker Medical tube was successfully placed, with presence of a Tusker Medical tube across the tympanic membrane in all successfully treated ears at the 3-week post-procedure follow-up visit.

The statistical test for the pivotal cohort Tube Retention secondary endpoint is a hypothesis test for the proportion of subjects with a Tusker tube in all successfully treated ears at the 3-week follow-up visit against a Tube Retention performance goal. A mid-P method for a single proportion will be used to test

$$H_0: p \leq 88\%$$

Vs.

$$H_a: p > 88\%.$$

This endpoint will be considered met if the p-value from the test is less than 0.025.

13.8. Handling Drop Outs or Missing Data

The number and proportion of subjects eligible for and compliant with all follow-up examinations will be presented. Subjects who withdraw from the study will be tabulated with the reasons for the withdrawal. Subjects who initiate the procedure, regardless of tolerability outcome or anesthesia effectiveness, will be encouraged to return for all follow-up assessments.

Sensitivity analyses and handling of missing data is described in the Statistical Analysis Plan CPR007004.

CPR007001 Rev E
Effective: 11/10/2017

A large black rectangular redaction box covers the majority of the page content. At the top, there are two smaller black rectangular redaction boxes, one on the left and one on the right. At the bottom, there is a single large black rectangular redaction box at the very bottom edge.

14.0 ETHICS/PROTECTION OF HUMAN SUBJECTS

Prior to enrolling subjects, all sites must have the approval of an Institutional Review Board (IRB) responsible for reviewing clinical studies at the study site. The IRB must also approve the subject Informed Consent and Assent as well as recruiting advertisements and subject-facing information. Amendments to any of these documents must also be approved by the IRB. No subjects will be consented or enrolled to a site until IRB approval has been received in writing. The Informed Consent process is described in **Section 11.5**.

14.1. Subject Confidentiality

Subject confidentiality will be maintained at all times during the study. A unique subject identifier will consist of (1) a Protocol Identifier, (2) an Investigational Site identifier, and (3) a consecutive subject number.

Example: 7001-JON-001

7001 = 4 digit Protocol Number

JON = Investigator [name]

001 = Number of subject enrolled

The Investigator or evaluation personnel at each study site will assign the subject code number and access to this code number will be restricted to the Investigator and evaluation personnel. The key to the subject code numbers and subject data collection sheets containing the subject's name and identification code will be securely maintained at each study site.

15.0 PREMATURE TERMINATION OR WITHDRAWAL

[figure not shown]
15.1. Subject Stopping Criteria

Subjects who do not complete the study procedure, will be encouraged to remain in the study to complete post-procedure evaluations. If a subject withdraws prematurely from the

study, a genuine effort must be made to determine the reason(s) why the subject failed to return for the procedure or follow-up visit or discontinued the study, and the reason must be recorded on the appropriate CRF.

Potential reasons for discontinuation include:

- Subject or subject's caregiver decides it is in the subject's best interest to withdraw
- Subject expresses intolerance or discomfort during the procedure and subject or subject's caregiver indicates they wish to stop the procedure and withdraw
- Investigator decides if a serious adverse event requires withdrawal from the study
- Investigator decides it is in the subject's best interest to be withdrawn if subject is experiencing intolerance or intolerable reaction to the procedure.

If a subject discontinues participation in the study, the Investigator will attempt to have the subject continue participation to complete follow-up assessments unless the subject's safety is compromised. All Serious Adverse Events that have not resolved by the end of the subject's participation in the study, must be followed until the event resolves, stabilizes or becomes non-serious.

All potential subjects in the study will be verbally informed and will sign an informed consent in compliance with 21CFR §50 that states that any withdrawal from the study will neither prejudice nor in any way affect their future treatment.

Prior to designating a subject as lost to follow-up, the site must provide documented evidence of three (3) good faith attempts to contact the subject to which there has been no response. At that point the subject will be considered lost-to-follow-up and withdrawn from the study.

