each investigator will enroll 2 lead-in subjects in-office undergoing tube placement using the TDS with local anesthesia facilitated by the Iontophoresis System (up to 100 subjects). Investigators may enroll into the pivotal cohort following completion of their lead-in procedures. The pivotal cohort will include 102 children ages 5 years and greater plus 120 children less than 5 years of age.

[figure not shown]
All pivotal and lead-in subjects will follow the same study protocol assessments and visit schedule consisting of a screening visit, procedure visit and a 3-week post-procedure follow-up visit. [REDACTED]

In addition, subjects will return for follow-up examinations every 6 months following the procedure until the tube implants have extruded, up to 24 months post-procedure. Otologic examination, tympanometry and audiometry will be conducted at the screening visit for all subjects (OR and in-office). Additionally, subjects treated in-office with local anesthesia (lidocaine iontophoresis) will undergo a cranial nerve physician exam at screening. The in-office lead-ins and pivotal cohort procedure will consist of local anesthesia of the tympanic membrane using the TULA Iontophoresis System with the lidocaine solution. Following iontophoresis, anesthesia of the TM will be assessed and tympanostomy tube placement will be conducted in anesthetized ears using the TULA Tube Delivery System. Subjects will return for a follow-up visit 3-weeks

ⁱ Subjects who are consented for the study will be considered enrolled. Throughout the protocol, enrollment numbers will reflect consented enrolled subjects with evaluable data. Enrolled subjects who are determined to be ineligible (screening failures), and enrolled subjects who withdraw prior to the study procedure are not included in the enrollment subject counts presented herein. Further definition of subjects included in the analysis sets is provided in Section 13- Statistical Methods

	post-procedure for otoscopic examination, tympanometry and audiometric assessment for all subjects with the addition of the cranial nerve exam for in-office subjects only. Follow-up assessments for tube duration at 6, 12, 18 and 24 months will consist of otoscopic examination and tympanometry. Lead-in procedures will be analyzed separately from the pivotal pediatric cohort.
Study Design:	Study Phase: Pivotal
	No. of Centers: Minimum of 15, maximum of 25 investigational centers
	Number of Arms: Single

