11.7.10. Unsuccessful Procedures

If the in-office procedure is not a success and the physician refers the subject for traditional OR TT placement, the Investigator will document the OR procedure TT placement success. Reasons for any OR procedural failures (of TT placement) will be documented. The OR procedure must take place within 2 months of the first in-office procedure. The subject must complete a post-procedure follow-up visit after the failed in-office procedure, at the protocol specified 3-week follow-up visit, or earlier if the OR procedure is planned prior to the 3-week visit. If no Tusker tube was placed, no additional follow-up visit is required following the subsequent procedure. If a Tusker tube was placed, the subject should follow the protocol-specified follow-up visit schedule to assess safety of the Tusker tube.

[REDACTED]

11.9.3-Week Post-Procedure Follow-Up Visit (+/- 7 Days)

[figure not shown]
1. All subjects are required to return for the 3-week post-procedure follow-up visit.
2. An otoscopic examination will be used to visually examine the condition of the external ear canal, TM, myringotomy, tube retention and patency.
3. The subject will complete the audiology and tympanometry, and cranial nerve physical exam (for in-office subjects only).
4. Subjects will be evaluated for any adverse events, and changes in concomitant medications will be recorded.

11.10. 6, 12, 18 and 24-month Post-Procedure Follow-Up Visits (+/- 28 days)

1. All subjects are required to return for additional follow-up visits through confirmation of tube extrusion (both ears if bilateral tube placement).
2. An otoscopic examination will be used to visually examine the condition of the external ear canal, TM, myringotomy, tube retention and patency.
3. The subject will complete tympanometry. If audiology is indicated, the study will collect audiometric data however there is no study requirement for audiology or audiology method for follow-up visits subsequent to the 3-week visit.
4. Subjects will be evaluated for any adverse events, and changes in concomitant medications will be recorded.
5. The subject will be exited from the study following confirmation of tube extrusion or completion of the 24 month visit if tube remains in place.

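### Section 15.1 lets a site withdraw a child as lost to follow-up after three unanswered contacts, with no renewed contact required at later visits and no stated route back

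*Protocol*

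**What the plan says.** Protocol Section 15.1 sets the condition for calling a child lost: "the site must provide documented evidence of three (3) good faith attempts to contact the subject to which there has been no response". The consequence follows directly: "At that point the subject will be considered lost-to-follow-up and withdrawn from the study". The rule does not depend on which visit was missed.

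The planned follow-up is longer. The Protocol Summary (Section 5.0) says "subjects will return for follow-up examinations every 6 months following the procedure until the tube implants have extruded, up to 24 months post-procedure", and gives the purpose and content of those visits: "Follow-up assessments for tube duration at 6, 12, 18 and 24 months will consist of otoscopic examination and tympanometry". Section 11.10 makes them mandatory: "All subjects are required to return for additional follow-up visits through confirmation of tube extrusion". It names two planned exits: "The subject will be exited from the study following confirmation of tube extrusion or completion of the 24 month visit if tube remains in place". Table 4 also schedules adverse event collection at each of these visits.

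Section 15.1 contains softening text as well. For a subject who discontinues, "the Investigator will attempt to have the subject continue participation to complete follow-up assessments unless the subject's safety is compromised". Sites must make an effort to learn why a subject did not return, and serious adverse events still open when participation ends must continue to be followed.

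**The concern.** Non-response and withdrawal are different things. A family that does not answer around the 6-month visit may still come at 12 months, and a later otoscopy keeps its value. If the tube is in place at 12 months then, barring replacement, it was in place at 6 months. If it is out, the time of extrusion is still bounded. A persisting perforation would also still be visible. Treating the first run of unanswered calls as withdrawal can turn one missing visit into the loss of all later ones.

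What is at stake is the 6-24 month information on tube duration and ear safety. The loss may be informative. Families of children who are well and families who have sought care elsewhere may both stop answering. These could pull in different directions, so no net direction of bias can be claimed. In a single-arm trial there is no comparator group against which selective loss would show.

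**Working it through.** The plan states no loss rate and no figure that depends on this rule, so there is nothing to reproduce. The check is a reading of the text followed by two illustrations on assumed rates.

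**1. What the text requires.**
- Trigger (15.1): three documented attempts without response. A missed visit alone is not enough.
- Not stated in the visible text: spacing of the attempts, a link to a visit window, a renewed attempt at the next scheduled visit, or readmission of a child who returns.
- The other reasons for discontinuation listed in 15.1 are active decisions by the subject, caregiver or investigator. Non-response is not, yet it is given the same status of withdrawn.
- The sentence on keeping discontinuing subjects in follow-up gives no procedure for a family that cannot be reached. The sentence on serious adverse events covers only children with an open one.

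**2. Visits at risk.** The schedule is 3 weeks, then 6, 12, 18 and 24 months. Scheduled visits left after a missed visit: four after 3 weeks, three after 6 months, two after 12 months, one after 18 months. These are maxima, because confirmed extrusion ends the visits.

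**3. Children lost who could have been kept (assumed rates).** Number = pivotal children × share implanted × share unreachable around one early visit × share of those who would attend a later visit if called.
- Pivotal children: 222 (Protocol Sections 5.0 and 10.3). The other three factors are assumptions: 85%, 5-15% and 30-70%.
- Implanted: 222 × 0.85 = 188.7.
- Unreachable: 188.7 × 0.05 = 9.4, up to 188.7 × 0.15 = 28.3.
- Recoverable: 188.7 × 0.05 × 0.30 = 2.8, up to 188.7 × 0.15 × 0.70 = 19.8. That is about 3 to 20 children.
- Central case: 188.7 × 0.10 × 0.50 = 9.4, about 9 children.
- With 68% implanted (the performance goal) in place of 85%: 222 × 0.68 = 151.0, and the range becomes 151.0 × 0.05 × 0.30 = 2.3 to 151.0 × 0.15 × 0.70 = 15.9, about 2 to 16.

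The up to 200 lead-in children (100 operating-room and 100 in-office) on the same schedule are not counted.

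**4. How the rule could compound (upper bound).** Let q be the assumed share of children who, at each visit, miss it and leave three contacts unanswered. With permanent withdrawal, (1 − q)^5 remain at the fifth visit (24 months). If every such child returned at the next visit, 1 − q would be seen.
- q = 2%: 0.98^5 = 90.4% against 98%, or 201 against 218 of 222.
- q = 5%: 0.95^5 = 77.4% against 95%, or 172 against 211.
- q = 10%: 0.90^5 = 59.0% against 90%, or 131 against 200.

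Full return is the most favourable alternative, and the calculation ignores children who exit after extrusion or never receive a tube. The gaps are therefore upper bounds.

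**The case against.** A reader might infer that three unanswered calls start an automatic clock and that one missed visit ends all follow-up. The documents do not support that. The three attempts are worded as a minimum that a site must document before it may designate a child lost. Nothing forbids more attempts, a later call or a returning child, and open serious adverse events are still followed. What remains is narrower: once the minimum is met, designation and withdrawal are permitted together, and nothing requires anyone to try again.

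A reader might also infer that 15.1 contradicts 11.10. It does not. Section 11.10 gives the planned schedule and exits, and 15.1 governs premature exit. Any loss-to-follow-up rule cuts a planned schedule short. The issue is that this one may cut it shorter than necessary.

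It is fair to add that three documented attempts is a defined and auditable standard, and that withdrawals are already tabulated with reasons (Protocol 13.8, SAP 7.0 and 17.0). Parts of both documents are blacked out, including SAP text between Sections 11.3 and 14 and around Section 17. Related provisions, and the analysis of tube duration itself, may exist there.

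**Conclusion.** The point holds as a cheap improvement, not as an error that threatens the trial's conclusions. As written, 15.1 can release a child who may still have a study tube from the 6-24 month tube-duration and safety visits after one missed visit and three unanswered contacts. The general sentence on retaining discontinuing subjects does not fill the gap for families who cannot be reached.

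A reader might go on to infer that the trial's main results are at risk. They are not. Procedural Success includes every child who starts iontophoresis, and Tube Placement Tolerability is scored at the procedure. Patency and retention use the 3-week visit, and SAP Section 17.0 excludes children who miss it whatever 15.1 says. No hypothesis test on the later visits is visible.

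The size is unknown. The range of about 3 to 20 pivotal children rests wholly on the assumed 85%, 5-15% and 30-70%, none of which comes from the documents.

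**What to change.** Amend Section 15.1 as follows:
- Record three unanswered attempts as a missed visit.
- Contact the family again at each later scheduled window, and accept a child who returns.
- Assign lost-to-follow-up only when the last applicable window has closed: 24 months for a child with a study tube and no confirmed extrusion, or the required post-procedure visit for a child without one.
- Record withdrawal only when the family or the investigator actively withdraws the child, and tabulate the two categories separately in the disposition table (SAP 7.0).

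The cost is a wording change and a few more calls per missed visit by existing site staff. The downside is that final lost-to-follow-up status is known later.

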15.2. Study Stopping Criteria

The Sponsor or Investigator may terminate the study or center participation at any time for reasonable cause, and will provide sufficient notification.

Reasons for premature suspension of the trial include, but are not limited to:

- Risk to Subjects

- Lack of effectiveness [REDACTED]
- Inadequate enrollment
- Business reasons

Reasons for premature termination of an investigational site include, but are not limited to:

- Site is non-compliant to protocol, procedures or GCP
- Inadequate enrollment

Reasons for premature suspension of enrollment include but are not limited to:

- 3 serious Grade 3 or higher unexpected drug, device or procedure-related adverse events.

[REDACTED]

[REDACTED]

At the point the site or study is terminated, the site will immediately invoke all procedures required at the 3-week follow-up visit.

All potential subjects in the study will be verbally informed, and will sign an informed consent in compliance with 21CFR §50 that states that study termination will neither prejudice nor in any way affect their future treatment.

16.0 INVESTIGATOR RESPONSIBILITIES

Investigators who participate in this study will conduct the study according to the protocol, the Declaration of Helsinki, GCP and applicable regulatory requirements. Tusker Medical will sponsor the conduct of the study at approximately 25 investigational centers. This study will be performed under the direction and responsibility of the physician investigator at each study site. It is the responsibility of the Investigators to ensure study material is reviewed and approved by all applicable Institutional Review Boards (IRB), hospital committees, and administrative personnel as required.

The Investigator is responsible for the execution of the study, proper performance of participating personnel, ensuring adherence to the protocol and schedule of procedures, and for the control of devices under investigation. The Investigator is also responsible for protecting the rights, safety, and welfare of subjects under the investigator's care, and ensuring that written informed consent is obtained.

The Investigator is responsible for data confidentiality, quality, and completeness, and proper data storage in a secure file for a period of time as indicated in the protocol, Clinical Trial Agreement (CTA) and if mandated, by the respective IRBs.

The Investigator and site personnel directly involved with the study will receive training in the protocol and use of devices prior to initiation of the study. This training will be

conducted by the Sponsor (Tusker Medical, Inc.) or designee, prior to initiation of the study.

18.0 MONITORING

Tusker Medical, Inc. (Sponsor) or designee will monitor the study sites to ensure investigators are in compliance with the protocol; subject informed consent forms are properly completed; adequate protection of the rights of the human subjects and the quality and integrity of the resulting data; study data is verified against source documents for key safety and effectiveness variables; investigational devices and drug are properly controlled; and verification that reports are filed in accordance with the protocol and the appropriate regulations. Monitoring will be conducted according to the Sponsor’s monitoring procedure and study monitoring plan.

19.0 INVESTIGATIONAL PRODUCT ACCOUNTABILITY

Access to investigational drug and devices shall be controlled and the investigational drug and devices shall be used only in the clinical investigation and according to the protocol. The Sponsor shall keep records to document the physical location of all investigational drug and devices from shipment to the investigation sites until return or disposal. Drug and devices will be stored according to product labeling. The principal investigator or an authorized designee shall keep records documenting the receipt, use, return, and disposal of the investigational drug and devices, which shall include (a) the date of receipt, (b) identification of each investigational drug and device (batch number/serial number or unique code), (c) the expiration date, (d) the date or dates of use, (e) subject identification, and (f) the date of return of unused, expired or malfunctioning investigational products, if applicable.

20.0 DEVIATIONS

A protocol deviation is defined as any event where the Investigator or site personnel deviate from the study protocol or study procedures for any reason. It is the Investigator's responsibility to ensure that there are no protocol deviations throughout the life of the study. In the event that a non-emergency protocol deviation is identified, at the time of identification, the personnel identifying the event will review and define appropriate corrective actions to prevent recurrence. The IRB will be notified as applicable. Any deviations from this protocol will be documented by the site on a protocol deviation CRF.

21.0 DATA HANDLING AND RECORD KEEPING

21.1. Source Data and Case Report Forms

All study data will be captured on source documents by the Investigational Site. Data from the source documents will be recorded to CRFs by site personnel that have been trained on the protocol and CRF completion.

